1 Original Trial Protocol

2 **Date of Application:** 2010-05-13

3 **Title of Study:** Depression, Estrogen Replacement, and Cardiovascular Health in the  
4 Perimenopause

5 **Name and degrees of Principal Investigator(s):** [name] & [name],  
6 M.D.

7 **Name of funding source or sponsor:** National Institute of Mental Health

8 **Amendments Made to the Following Protocol:**

9 **Unless otherwise stated, the following changes were made to the study exclusion criteria to**  
10 **facilitate participant recruitment:**

- 11 • Women with borderline elevated LDL (190 – 200 mg/dl) at baseline were allowed to enter  
12 the trial if their physician was not intending to treat them over the course of the subsequent  
13 12 months **(2010-11-16)**.
- 14 • Early postmenopausal women (in STRAW +1b) were allowed to enter the trial **(2010-12-**  
15 **30)**.
- 16 • Women with a history of >1 biopsy were allowed to enter the trial if there was no personal  
17 or family history of breast cancer in the first or second degree relatives and if the  
18 documented histologic findings for all biopsies were consistent with the following:  
19 fibrocystic changes (within the normal range - cysts and ductal ectasia, mild hyperplasia,  
20 nonsclerosing adenosis, and periductal fibrosis, simple fibroadenoma, and miscellaneous  
21 (lobular hyperplasia, juvenile hypertrophy, and stromal hyperplasia)); benign tumors  
22 (hamartoma, lipoma, phyllodes tumor, solitary papilloma, neurofibroma, giant adenoma, and  
23 adenomyoepithelima); traumatic lesions (hematoma, fat necrosis, and lesions caused by  
24 penetration by a foreign body); infections (granuloma and mastitis); sarcoidosis; metaplasia  
25 (squamous and apocrine); diabetic mastopathy **(2010-12-30)**.
- 26 • The requirement that all women have an FSH level >2 SD above mean premenopausal levels  
27 was removed **(2011-02-17)**.
- 28 • Women without a uterus but with at least one ovary retained were allowed to enter the trial  
29 if: 1) they were experiencing vasomotor symptoms and their baseline estradiol levels were  
30 above postmenopausal concentrations (> 40 pg/ml) or, 2) they were not experiencing  
31 vasomotor symptoms but had baseline estradiol > 40 pg/ml and baseline FSH levels > 14  
32 pg/ml, which is two standard deviations above the mean level of a previously-recruited  
33 sample of reproductive-aged women, in line with STRAW staging guidelines **(2011-03-04)**.
- 34 • If a participant knew the complete family history for the mother's side but none or only  
35 partial history for the father's side, it was decided that the study gynecologist would evaluate  
36 whether transdermal estradiol would be contraindicated based on the history provided – if  
37 not, she could enter the trial **(2012-09-20)**.
- 38 • Women with a single episode of past depression were considered eligible if their single  
39 episode met the following criteria: the duration was at least 3 months, at least 6 of 9 MDD

- 40 symptoms were experienced (exceeding the required 5-symptom threshold), and the episode  
41 occurred as an adult (not in childhood or early adolescence) **(2013-08-05)**.
- 42 • The acceptable age range extended from 45-55 to 45-60 **(2014-02-27)**.
  - 43 • The exclusion criteria related to psychiatric history were changed to exclude women with:  
44 history of suicide attempts; history of bipolar and related disorders or schizophrenia  
45 spectrum and other psychotic disorders; history of severe substance use if it was in the past  
46 10 years; less than two years in remission from substance use disorders, bulimia nervosa,  
47 anorexia nervosa, or posttraumatic stress disorder; current psychiatric diagnosis of binge  
48 eating disorder, a neurodevelopmental disorder, or a trauma- and stress-related disorder  
49 (except for posttraumatic stress disorder) with severity greater than mild **(2014-02-27)**.
  - 50 • Women having had a bilateral oophorectomy were allowed into the trial if the procedure had  
51 occurred within 24 months and the participant had been menstruating regularly prior to the  
52 procedure **(2014-02-27)**.
  - 53 • The requirement of having a baseline CES-D score  $\leq 8$  was increased to  $\leq 16$  **(2010-11-16)**  
54 and later removed altogether **(2014-02-27)**.
  - 55 • The acceptable body mass index range was lowered to  $<30$  due to concerns that estradiol  
56 therapy may be less safe in obese women **(2011-08-18)** but was later increased to  $<35$  based  
57 on research suggesting that transdermal estradiol, specifically, was not related to an  
58 increased health risk in these women **(2014-04-04)**.

59

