#### 60 **Changes made to study protocol:**

- 61 • Rather than starting a participant on 0.1 mg of estradiol immediately, the protocol was  
62 changed so that participants started on 0.025 mg for two weeks, then 0.05 mg patch for the  
63 next four weeks, and a 0.1 mg patch for the remainder of the study **(2011-02-14)**.
- 64 • To avoid very heavy bleeding following progesterone administration, the schedule for  
65 administering progesterone was changed from every three months to every two months  
66 **(2011-07-08)**.
- 67 • Participant compensation was increased to \$1325 when study visits at months 6 and 12  
68 began occurring separately from the months 6 and 12 laboratory visits **(2012-05-15)**.
- 69 • Following randomization, participants were given the option to participate in four follow-up  
70 phone calls in which the CES-D was administered (months 15, 18, 21 and 24) for an  
71 additional \$100 in compensation **(2012-05-15)**.

72

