#### 73 **Brief Summary**

74 Purpose: The purpose of this study is threefold: 1) to examine cardiovascular risk factors in  
75 perimenopausal women with or without histories of recurrent depression; and the role of  
76 cumulative trauma exposure in the relationship of histories of depression to cardiovascular  
77 risk; 2) to examine progression in cardiovascular risk and the development of depressive  
78 episodes over 12 months in perimenopausal women with or without a history of recurrent  
79 depression who are not being treated with estradiol replacement therapy (ERT); and 3) to  
80 examine predictors and mediators of ERT - related treatment efficacy for both depression and  
81 cardiovascular risk.

82 Participants: Three hundred and twenty (320) women, 45 – 55 years of age undergoing a natural  
83 perimenopause ( $\geq 2$  skipped cycles and an interval of amenorrhea  $\geq 60$  days with FSH  $> 2$   
84 SD above mean premenopausal levels) will be tested such that half ( $n= 160$ ) will have a  
85 history of recurrent DEP (2+ episodes of depression, at least one of which is major  
86 depression) but be in remission, while the other half will be recruited as never depressed  
87 controls, matched for age and current low depressive symptoms ( $\leq 8$  on the CES-D 20-item  
88 depression scale). All subjects will be medically healthy perimenopausal women, 45 – 55  
89 years of age with no contraindications for ERT.

90 Procedures (methods): Subjects will be tested at baseline for indices of cardiovascular risk  
91 (cardiovascular stress reactivity, metabolic risk, cardiac autonomic tone, and endothelial  
92 function) and for depressive symptoms, functional impairment, menopausal symptoms,  
93 negative life events, diet and exercise. Lifetime trauma exposure will also be determined.  
94 Using a placebo-controlled, double-blind design, following baseline assessments, half of the  
95 women in each group (history of depression or never depressed) will be randomized to either  
96 transdermal  $17\beta$ -E2 (100ug/day) or placebo for 12 months (oral micronized progesterone will  
97 be given every 3 months to women on active ERT to protect the endometrium and placebo  
98 progesterone given to women on placebo ERT). Subjects will be assessed at months 1, 2, 4,  
99 6, 8, 10 and 12 for compliance, vitals, side effects, depressive symptom severity and  

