## 302 **Study Design, Methods and Procedures**

303 **Overview of Protocol:** Briefly, medical and psychiatric evaluations will be conducted during an  
304 initial Screening period. Eligible women will then undergo initial Baseline Pretreatment  
305 assessments, including stress reactivity testing and assessments of baroreceptor sensitivity and  
306 endothelial function. Following Time 1 assessments, women will be randomized (in a 1:1  
307 fashion) to either transdermal 17 $\beta$ -estradiol (100 ug/day) or placebo for 12 months. Following  
308 randomization, during months 1, 2, 4, 6, 8, 10 and 12, compliance, side effects, vitals, depression  
309 symptoms and functional impairment will be assessed. Also, on a quarterly basis, oral  
310 micronized progesterone (200 mg/day x 12 days) will be given to ERT treated women. At the  
311 end of month 6 (Time 2 testing) and month 12 (Time 3 testing), while estradiol is still on board  
312 but prior to the final progesterone administration, all assessments conducted at baseline will be  
313 repeated. These events are described below.

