### 314 **D.3. Procedures**

#### 315 **I. Screening Medical and Psychiatric Evaluations**

316 Following the informed consent process, subjects will complete a detailed medical and  
317 medication history form (enclosed); demographic data and height, weight and waist  
318 circumference will be obtained. Questionnaires assessing functional impairment, sleep quality  
319 and climacteric symptoms, diet and physical activity level will be administered (enclosed). The  
320 CES-D scale will also be administered. CES-D scores  $\geq 9$  will result in exclusion and referral  
321 for further evaluation. Stethoscopic BP will also be taken. Using JNC 7 guidelines, women  
322 exhibiting Stage 1 or Stage 2 hypertension (HTN) (140+ mmHg SBP and/or 90+ mmHg DBP)  
323 will be excluded and referred. Women will also have a fasting blood draw to determine FSH,  
324 plasma lipids (HDL-C, LDL-C, and triglycerides), and fasting glucose. As per the National  
325 Cholesterol Education Program (NCEP) and American Diabetes Association guidelines, fasting  
326 LDL  $\geq 190$  mg/dl or fasting glucose  $\geq 7.0$  mmol/l (126 mg/dl) (exclusionary) will prompt a  
327 referral. See A.4.8. for monitoring of change in health status during the course of the study.

328

329 Subjects meeting medical and psychiatric screening criteria will have a psychiatric evaluation  
330 with clinical psychologist [name], who will administer the Structured Clinical Interview for  
331 DSM-IV (SCID-NP with psychotic screen) for Axis I disorders and who will administer the  
332 cumulative trauma interview. Any woman meeting criteria for a current Axis I disorder will be  
333 excluded and referred for treatment. Women meeting psychiatric inclusion criteria will be  
334 scheduled for a gynecological exam with [name] who will take a complete medical history,  
335 including a history of estrogen-dependent neoplasia, a history of thrombophlebitis or  
336 thromboembolic disorders, gall bladder disease, liver dysfunction or other disorders for which  
337 estradiol or progesterone use is contraindicated. He will also perform a pelvic exam as well as  
338 endometrial ultrasound to confirm that they are free of any signs or history of endometrial  
339 disorder, abnormal uterine anatomy (e.g. fibroids), abnormal ovarian anatomy (e.g.  
340 endometrioma). If the endometrium is  $> 4$  mm, a routine endometrial biopsy will be performed  

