409 pressure (approximately 200 mmHg) for 5 min. Images of the artery will be recorded for 2 min  
410 after cuff deflation. In order to confirm that any treatment-associated changes in flow mediated  
411 dilatation result from enhanced endothelial function, after 10 min of rest, a second baseline  
412 image will be acquired. Then, sublingual nitroglycerin spray (0.4 mg) will be administered to  
413 determine endothelium-independent vasodilation, and ultrasound images will be acquired for the  
414 subsequent 5 min. Flow-mediated and nitroglycerine-mediated dilation will be calculated as  
415 percentage changes in diameter from their respective baselines.

416 **III. Randomization and Pharmacological Intervention Procedures**

417 Under double-blind procedures, subjects will be randomized to receive either transdermal 17 $\beta$ -  
418 estradiol or placebo (as inert patches) for 12 months, stratified based on histories of recurrent  
419 depression (yes, no). The study statistician, [name] will be responsible for creating the  
420 randomization scheme, and the UNC Hospitals Investigational Drug Services will manage the  
421 randomization and dispensing of all study medication in blinded form. The use of specially  
422 prepared patches with no outer label will allow both the subject and the experimenter to be blind  
423 to the intervention. For those 160 women randomized to receive transdermal estradiol, each will  
424 wear a patch (Climara®) designed to deliver 0.10 mg estradiol over a 24 hour period.  
425 Transdermal administration of estradiol produces mean serum concentrations of estradiol  
426 comparable to those produced by premenopausal women in the early follicular phase. Climara®  
427 continuously releases estradiol, which is transported across the intact skin leading to sustained  
428 circulating levels of estradiol during each 7-day treatment period. For the 160 women  
429 randomized to placebo, each will receive a placebo patch identical in appearance to the active  
430 patch (developed by 3M Pharmaceuticals).

431 **IV. 12 Month Intervention Phase**

432 Procedures during the Intervention: A monthly calendar outlining weekly schedules for changing  
433 patches, study visits, and the monthly schedule for taking micronized progesterone or placebo  
434 progesterone will be provided. Study visits will occur on months 1, 2, 4, 8, and 10 to allow for  

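### Women without a uterus became eligible on 2011-03-04, but the documented progesterone rule does not exempt those on active ERT

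*Protocol*

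**What the plan says.** The eligibility entry dated 2011-03-04, in the list of amendments at the front of the protocol, reads "Women without a uterus but with at least one ovary retained were allowed to enter the trial". It attaches conditions on estradiol and, for women without vasomotor symptoms, on FSH. It says nothing about study drug.

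Active progesterone is assigned to the active arm as a whole. The Brief Summary has it "be given every 3 months to women on active ERT to protect the endometrium". The Overview of Protocol says that "micronized progesterone (200 mg/day x 12 days) will be given to ERT treated women". Progesterone Administration, under the 12 Month Intervention Phase, gives the same assignment and dose, and names prevention of endometrial hyperplasia as the purpose. Protection Against Risk again gives an endometrial reason.

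The log records one later change to this rule, on 2011-07-08: "To avoid very heavy bleeding following progesterone administration, the schedule for" "administering progesterone was changed from every three months to every two months". It changes the interval and names no subgroup.

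Progesterone Administration also says that every woman takes a blinded capsule in the last 12 days of each month. The placebo arm always takes placebo, and the active arm takes placebo in the months without an active course.

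**The concern.** The original entry criteria required a natural perimenopause with skipped cycles, so every woman on active ERT could be assumed to have a uterus, and a rule covering the whole arm was coherent. The 2011-03-04 amendment removed that assumption, and the dosing rule shown was not adapted to it.

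What is at stake is exposure of participants. The risk section lists breast tenderness, dizziness, abdominal bloating and chest pain among the common side effects of progesterone. A woman without an endometrium bears these without the benefit that justifies the drug. The protocol's own reasoning points the same way: it chose intermittent dosing because that is enough for safety, and because progestins counteract much of estrogen's cardiovascular benefit. For a woman without a uterus, the amount needed for endometrial safety is none.

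**Working it through.** The protocol states no figure on this point, so there is none to reproduce. The check is a reading of the rules together, followed by exposure arithmetic.

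**Rules side by side**

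| Element | Place in the protocol | Content |
|---|---|---|
| Who may enter | Amendment of 2011-03-04 | Women without a uterus, at least one ovary retained |
| Who takes active progesterone | Brief Summary; Overview of Protocol; Progesterone Administration | All women on active ERT |
| Why | Brief Summary; Progesterone Administration; Protection Against Risk; endometrial cancer paragraph of the risk section | Endometrial protection only |
| Later change | Changes made to study protocol, 2011-07-08 | Interval from three to two months, because of heavy bleeding |
| Exemption | None found | – |

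Protection Against Risk also mentions avoiding other progestins. That explains why micronized progesterone was chosen, not why a woman without a uterus would need it. The heavy-bleeding reason for the 2011-07-08 change also presupposes a uterus.

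**Exposure per affected woman on active ERT over 12 months**

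Inputs: 200 mg/day for 12 days per course (Overview of Protocol; Progesterone Administration), and one active course every two months (2011-07-08 entry). The three-month interval stayed in force for only 126 days after these women became eligible (2011-03-04 to 2011-07-08), so the two-month interval is the relevant one.

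- Courses: 12 / 2 = 6
- Days: 6 × 12 = 72
- Share of the year: 72 / 365 = 19.7%
- Dose: 72 × 200 mg = 14,400 mg = 14.4 g

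Six is an upper limit, since it requires completing the 12 months, including the course that follows the last testing. The log does not say which months carry active courses, but the total does not depend on that. Under an exemption the figures are 0 days and 0 g.

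**Effect on outcomes**

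Study visits fall in the first two weeks of the month, before the capsules. Laboratory testing at months 6 and 12 also comes before that month's course; for the last one the Overview says "but prior to the final progesterone administration, all assessments conducted at baseline will be" repeated. Measurements are therefore not taken during a course, and little bias is expected.

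**The case against.** The strongest reply is that this argues from silence. The amendments are brief summaries, and the 2011-03-04 entry stands in a list of changes to eligibility, where a dosing rule would not be expected. The body is the original text. Its dosing instruction carries its purpose, which a reader could take as limiting it to women with an endometrium, and a study gynecologist examines every woman. Much of this stands: an exemption may have been written or applied, and the documents cannot exclude it. A stated purpose is still not a dispensing instruction, however, and the protocol describes no route by which uterus status would reach the drug service.

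A second reply is that one regimen for the whole active arm is cleaner, and that intermittent dosing already avoids a continuous progestin for everyone. That is a fair design preference, but the protocol never gives it as a reason.

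A reader might also infer more than the documents support:

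- That women without a uterus actually received progesterone. Only the written rule is shown, not what was dispensed.
- That the treatment comparison is biased. The timing of visits and testing speaks against this.
- That the three-month wording left in the body is itself an error. It is original text beside an amendment log, and such a difference is not a fault.
- That the hormone-therapy hazard ratios in the risk section measure the harm here. They concern other regimens.

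**Conclusion.** The point holds as a minor gap in a treatment rule. The protocol admits women without a uterus, and the progesterone rule shown would give those on active ERT up to 6 courses (72 days, 14.4 g) in a year with no stated indication. This rests on the two-month interval, full completion of the 12 months, and the absence of an exemption in amendment text not shown.

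The number of affected women is not given and may be small, so no trial total is offered. The randomized comparison and the planned analyses remain sound.

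**What to change.** Add to Progesterone Administration:

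> Active progesterone is given only to women on active ERT who have a uterus. Women on active ERT without a uterus take placebo progesterone capsules every month.

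Record uterus status at the gynecological exam, which is already done by the study gynecologist, "who will take a complete medical history". Pass it to Investigational Drug Services at randomization, since that service already manages allocation and blinded dispensing. In the report, give the number of women who received estradiol alone.

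The cost is one rule, one data field and one descriptive count. No new product is needed, because placebo capsules are already dispensed. The blind is kept, because all women already take a capsule each month. Randomization and the analysis models do not change. The real downside is a mixed active arm: estradiol alone in women without a uterus and estradiol with intermittent progesterone in the rest, divided by a factor that is not a randomization stratum. If an exemption already exists in the full amendment text, stating it in the protocol is enough.

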#### 60 **Changes made to study protocol:**

- 61 • Rather than starting a participant on 0.1 mg of estradiol immediately, the protocol was  
62 changed so that participants started on 0.025 mg for two weeks, then 0.05 mg patch for the  
63 next four weeks, and a 0.1 mg patch for the remainder of the study **(2011-02-14)**.
- 64 • To avoid very heavy bleeding following progesterone administration, the schedule for  
65 administering progesterone was changed from every three months to every two months  
66 **(2011-07-08)**.
- 67 • Participant compensation was increased to \$1325 when study visits at months 6 and 12  
68 began occurring separately from the months 6 and 12 laboratory visits **(2012-05-15)**.
- 69 • Following randomization, participants were given the option to participate in four follow-up  
70 phone calls in which the CES-D was administered (months 15, 18, 21 and 24) for an  
71 additional \$100 in compensation **(2012-05-15)**.

72

#### 73 **Brief Summary**

74 Purpose: The purpose of this study is threefold: 1) to examine cardiovascular risk factors in  
75 perimenopausal women with or without histories of recurrent depression; and the role of  
76 cumulative trauma exposure in the relationship of histories of depression to cardiovascular  
77 risk; 2) to examine progression in cardiovascular risk and the development of depressive  
78 episodes over 12 months in perimenopausal women with or without a history of recurrent  
79 depression who are not being treated with estradiol replacement therapy (ERT); and 3) to  
80 examine predictors and mediators of ERT - related treatment efficacy for both depression and  
81 cardiovascular risk.

82 Participants: Three hundred and twenty (320) women, 45 – 55 years of age undergoing a natural  
83 perimenopause ( $\geq 2$  skipped cycles and an interval of amenorrhea  $\geq 60$  days with FSH  $> 2$   
84 SD above mean premenopausal levels) will be tested such that half ( $n= 160$ ) will have a  
85 history of recurrent DEP (2+ episodes of depression, at least one of which is major  
86 depression) but be in remission, while the other half will be recruited as never depressed  
87 controls, matched for age and current low depressive symptoms ( $\leq 8$  on the CES-D 20-item  
88 depression scale). All subjects will be medically healthy perimenopausal women, 45 – 55  
89 years of age with no contraindications for ERT.

90 Procedures (methods): Subjects will be tested at baseline for indices of cardiovascular risk  
91 (cardiovascular stress reactivity, metabolic risk, cardiac autonomic tone, and endothelial  
92 function) and for depressive symptoms, functional impairment, menopausal symptoms,  
93 negative life events, diet and exercise. Lifetime trauma exposure will also be determined.  
94 Using a placebo-controlled, double-blind design, following baseline assessments, half of the  
95 women in each group (history of depression or never depressed) will be randomized to either  
96 transdermal  $17\beta$ -E2 (100ug/day) or placebo for 12 months (oral micronized progesterone will  
97 be given every 3 months to women on active ERT to protect the endometrium and placebo  
98 progesterone given to women on placebo ERT). Subjects will be assessed at months 1, 2, 4,  
99 6, 8, 10 and 12 for compliance, vitals, side effects, depressive symptom severity and  
100 functional impairment (also menopausal symptoms, diet, and exercise). At months 6 and 12,  
101 all CV risk measures conducted at the baseline (described above) will be repeated.

